Statistical methods	
The purpose of this trial is to demonstrate proof of concept of clinical activity of BI 685509 on the primary endpoint. For the proof of concept an evaluation of the benefit of BI 685509 compared to placebo will be conducted.
 
To account for the repeated nature of the primary endpoint data and the covariates in the model, MMRM analysis will be carried out for change from baseline of log transformed UACR measured in 10-hour urine after 20 weeks of trial treatment in each patient group. The analysis will include the fixed, categorical effect of treatment at each visit, and the fixed continuous effects of baseline log transformed UACR at each visit. Visit will be treated as the repeated measure with an unstructured covariance matrix used to model the within-patient measurements. The adjusted mean change from baseline (and the related standard error) will be calculated for each group and will be used for the MCPMod to determine therapeutic dose. The analyses for dose-finding will be performed using MCPMod whereby several possible dose response models (patterns) will be evaluated to identify the best-fitting model or subset of models.
 
Regarding analyses of the secondary endpoints,
 
 1. MMRM will be used for the analysis for the change of UACR in First Morning Void.

	2. Descriptive statistics will be provided for the change of UACR in First Morning Void urine/10-hour urine and the UACR response rate along with figures.
--	--

FLOW CHART

Please refer to the [UACR AND EGFR SAMPLING FLOW CHART](#) as well as [FLOW CHART FOR PROCEDURES](#) that follow the main visit flow chart for specific sampling timepoints.

Procedures should be performed in the order they appear in this flow chart.

Trial Period	Screening			Baseline Run-in ^x		Randomised Treatment						Follow Up Period ⁱ			
	1 ⁱⁱⁱ	2	Home sampling without visit	End of Baseline/ Start of Treatment 3 ^{ix}	4 ^v	5 ^v	6	7	8	Home sampling without visit	EoT ^{vi} Start of FUp	FUp1	FUp2	Home sampling without visit	FUp3
Visit may be at patient's home ^{vii}		X					X	X	X				X		X
Telemedicine Contact ^{viii}		X	(X)				O			(X)		X	O	(X)	
Weeks before or after Visit 3	-5	-2	-1	0	2	4	6	12	18	19	20	21	22	23	24
Days	-35	-14	-7	1	15	29	43	85	127	134	141	148	155	162	169
Time window for visits (days)		+/- 2	+/- 2	none	+ 2	+ 2	+/- 2	+/- 4	+/- 2	+/- 2	+/- 2	+3	+/- 2	+/- 2	+/- 3
				Pre-dose											
Informed consent ^{ix}	X														

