Demographics, medical history including historical creatinine data, baseline conditions	X			X											
Check of in-/exclusion criteria	X ^z			X											
Concomitant therapies	X	X		X	X	X	X	X	X		X	X	X		X
Height	X														
Weight	X			X			X				X		X		X
Physical examination	X			X			X				X		X		
Vital signs	X	X		X ^{xi}	2X ^{xi}	3X ^{xi}	3X ^{xi}	3X ^{xi}	3X ^{xi}	3X ^{xi}	X		X		X

Proprietary confidential information © 2022 Boehringer Ingelheim International GmbH or one or more of its affiliated companies

Trial Period	Screening	Baseline Run-in ^x		Randomised Treatment								Follow Up Period ⁱ				
		1 ⁱⁱⁱ	2	Home sampling without visit	End of Baseline/ Start of Treatment 3 ^{ix}	4 ^v	5 ^v	6	7	8	Home sampling without visit	EoT ^{vi} Start of FUp	FUp1	FUp2	Home sampling without visit	FUp3
Visit ⁱⁱ																
Visit may be at patient's home ^{vii}		X					X	X	X				X			X
Telemedicine Contact ^{viii}		X	(X)				O			(X)		X	O	(X)		
Weeks before or after Visit 3	-5	-2	-1	0	2	4	6	12	18	19	20	21	22	23	24	
Days	-35	-14	-7	1	15	29	43	85	127	134	141	148	155	162	169	
Time window for visits (days)		+/- 2	+/- 2	none	+ 2	+ 2	+/- 2	+/- 4	+/- 2	+/- 2	+/- 2	+3	+/- 2	+/- 2	+/- 3	
				Pre-dose	Post-dose											
12-lead electrocardiogram (ECG), local assessment ^{xii}	X			X	2X	3X	3X	3X	X	X	X		X			
Safety laboratory (blood, urine)	X	X		X		X	X	X	X	X	X		X		X	
eGFR ^{xiii}	X	X		X		X	X	X	X	X	X		X		X	
PK sampling ^{xiv}				X	3X	4X	4X	4X	4X	4X	X					
Biomarker sampling (urine, serum and plasma)				X				X	X		X				X	
Pharmacogenomic sampling				X ^{xv}												
Optional biobanking sampling (serum, plasma, urine) ^{xvi}				X				X	X		X				X	
Pregnancy test ^{xvii}	X			X				X	X	X	X					
Spot urine (UACR)	X ^{xviii}															
Train patient on UACR and [REDACTED]	X															
Provide home sampling kit ^{xix}	X	X			X	X	X	X	X	X	X		X			
UACR First Morning Void		X	X	X		X		X	X	X	X		X	X	X	
UACR 10-hour urine sample		X	X	X		X		X	X	X	X		X	X	X	

Proprietary confidential information © 2022 Boehringer Ingelheim International GmbH or one or more of its affiliated companies

Trial Period	Screening	Baseline Run-in ^x		Randomised Treatment								Follow Up Period ⁱ				
		1 ⁱⁱⁱ	2	Home sampling without visit	End of Baseline/ Start of Treatment 3 ^{iv}	4 ^v	5 ^v	6	7	8	Home sampling without visit	EoT ^{vi} Start of FUp	FUp1	FUp2	Home sampling without visit	FUp3
Visit ⁱⁱ																
Visit may be at patient's home ^{vii}		X					X	X	X				X			X

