									Start Tx	Up-titration 1		Up-titration 2										End Tx														
Days before visit	0	2	1	0	8	7	2	1	0	2	1	0	0	2	1	0	2	1	0	2	1	0	8	7	2	1	0	2	1	0	8	7	2	1	0	
First Morning Void (FMV)		X	X		X	X	X	X		X	X			X	X		X	X		X	X		X	X	X	X		X	X		X	X	X	X		
10-hour urine Sample after FMV		X	X		X	X	X	X		X	X			X	X		X	X		X	X		X	X	X	X		X	X		X	X	X	X		
Bring samples to clinic visit or pick-up at home*				X		X			X			X				X				X				X		X			X				X			
■ days before planned Visit 3, ▲ days before regular EoT at week 20, ● days before FU3, * When samples are picked-up from home, this will be after the 10 hour sampling is complete, which at the latest will be the following day.				■	■				■		■	■				■				■				■		■			■				■			

■ days before planned Visit 3, ▲ days before regular EoT at week 20, ● days before FU3, * When samples are picked-up from home, this will be after the 10 hour sampling is complete, which at the latest will be the following day.

FLOW CHART FOR PROCEDURES

In all instances when an ECG and blood samples are required at the same timepoint the ECG must be performed prior to the blood sampling and after the patient has been in the supine position for 5 minutes. Vital signs and ECGs must always be performed with sufficient time to allow the PK samples to remain within the time windows specified below.

Visit	Day See main flow chart for visit windows	PK Sampling Time Relative to Administration (morning dose) at Visit hh:mm	Time Point [hh:min]	Event	PK Sample No.
3	1	Prior to first PK blood draw and drug administration		Urine samples ¹ , weight and Physical Exam, Vital signs then ECG and then blood samples (other than PK)	---
		Within 30 minutes prior to drug administration	Just before drug administration	PK Blood	1
		0:00	0:00	Drug administration	---
		0:30 (+/- 5 min)	0:30	Vital signs then PK Blood	2
		1:00 (+10 min)	1:00	ECG then PK Blood	3
		2:00 ² (+ 15 min)	2:00	Vital signs then ECG then PK Blood	4
4	15	Prior to first PK blood draw and drug administration		Urine samples ¹ , Vital signs then ECG and then blood samples (other than PK)	---
		Within 30 minutes prior to drug administration	335:30	PK Blood	5
		0:00	336:00	Drug administration	---
		0:30 (+/- 5 min)	336:30	Vital signs then PK Blood	6
		1:00 (+ 10 min)	337:00	ECG then PK Blood	7
		2:00 ² (+ 15 min)	338:00	Vital signs then ECG then PK Blood	8
5	29	Prior to first PK blood draw and drug administration		Urine samples ¹ , Vital signs then ECG and then blood samples (other than PK)	---

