7.2 PLANNED ANALYSES

7.2.1 General considerations

The following analysis sets will be defined for statistical analyses:

Entered Set (ES): This patient set includes all patients who signed informed consent. The ES will be used for the analysis of patient desposition.

Randomised Set (RS): This patient set includes all entered and randomised patients. The RS will be used for the analyses of protocol deviations as well as demographics and baseline characteristics.

Treated Set (TS): This patient set includes all patients who received at least one dose of study medication. The TS is used for safety analyses and exposure.

Full Analysis Set (FAS): The patient set includes all patients who had at least one baseline measurement of UACR in week -2, -1, or 0 and at least one post-baseline measurement after week 6. The FAS is the main analysis set for the analysis of efficacy.

The pharmacokinetic set (PKS): This patient set includes all patients in the TS who provide at least one PK parameter that was not excluded because of protocol deviations relevant to the statistical evaluation of PK endpoints as defined in [section 5.3](#).

Further Analysis Sets will be defined in the TSAP, if needed.

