7.2.2 Primary endpoint analyses

The primary objectives are to demonstrate a non-flat dose response curve, evaluate the quantitative treatment effect size, and evaluate the dose-response relationship. The primary analysis will be performed on the FAS.

For the proof of concept (PoC) and dose finding, both multiple comparison procedures and modelling techniques (MCPMod) will be applied. The primary estimand of interest is the treatment effect using a primary approach. In the primary approach, trial medication is assumed to be taken as randomised and an intercurrent event is defined as an event of treatment discontinuation, death, or dropin/dropout of SGLT2i. The primary approach for primary analysis will include all data prior to intercurrent event. Any data collected after the intercurrent event will not be included in the primary analysis. The resulting missing data will be assumed to be missing at random (MAR).

The three different approaches for handling ICEs are summarized in the [Table 7.2.2: 1](#) below.

Table 7.2.2: 1 Summary of strategies for handling ICEs

Estimand strategy name	Treatment	ICE handling
Primary approach	Randomised treatment	Study med d/c: include data prior to study med d/c. Death: include data prior to death. SGLT2i initiation/discontinuation: include data prior to SGLT2i start/stop.

Table 7.2.2: 1 Summary of strategies for handling ICEs cont.

Estimand strategy name	Treatment	ICE handling
[REDACTED]	[REDACTED]	[REDACTED]
[REDACTED]	[REDACTED]	[REDACTED]

Treatment effect

The primary analysis will first address a dose relationship between doses of BI 685509 and placebo. The analysis will include the fixed, categorical effect of treatment at each visit, and the fixed continuous effects of baseline log transformed UACR at each visit. Visit will be treated as the repeated measure with an unstructured covariance structure used to model the within-patient measurements.

To conduct multiple comparison in MCPMod across doses, covariate adjusted fixed effect estimates of average response for each dose group and the covariance matrix will be extracted from the fit by the following MMRM and used for MCPMod analysis.

Statistical model (MMRM):

$$y_{ijklm} = \beta_j U_i + \tau_{jk} + \eta_l + \psi_m + e_{ij},$$

where

$$e_{ij} \sim N(0, \Sigma),$$

y_{ijkm} = reduction in log transformed UACR at visit j from baseline for subject i in stratum m ($m=1,2$) receiving treatment k ($k=1,\dots,4$),

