4. CHANGES IN THE PLANNED ANALYSIS OF THE STUDY

This section is not applicable as no change has been made.

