6.6.2 Efficacy data

6.6.2.1 Primary endpoint

Missing data for primary analysis will not be imputed:

- If some UACR value(s) for UACR at baseline is (/are) missing, all available UACR samples in week -2, -1, and 0 will be used to derive UACR at baseline.
- If any UACR value after randomisation is missing, the missing UACR will not be imputed; missing UACR due to ICEs will not be imputed.

The Mixed-effect Model for Repeated Measures (MMRM) approach used for the primary analysis (see [Section 7.4.1](#)) allows for missing data, assuming the missing data mechanism is ignorable. Even patients with only one post-baseline assessment can be included in the model and can, therefore, participate in variance estimation. The statistical model assumes that patients who had an ICE would have behaved similarly to those who remained in the study. The table below describes how/when to derive UACR values for MMRM:

Table 6.6.2.1: 1 Principal rule of UACR derivation for MMRM

UACRs for MMRM	UACR at baseline	UACR at visit 6	UACR at visit 7	UACR at EoT
Visits need to be included	First Morning Void (FMV) or 10-hour urine UACR baseline is defined as the mean of all non-missing assessments from Visit 2 until prior to the first intake of trial medication.	All available scheduled visits at visit 6	All available scheduled visits at visit 7	All available scheduled visits between visit 8 and EoT
Derivation	Average of all available UACR measurements defined at each visit			

Note: all available/scheduled UACR measurements will be used: no imputation for missing UACR measurement; this rule will be applied to FMV and 10-hour urine samples, respectively.

Sensitivity analyses will be conducted to investigate the potential effect of ICE handling approaches on the results of the primary analysis. Details about implementation of the sensitivity statistical analyses are described in [Section 7.4](#).

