7.4 PRIMARY ENDPOINT(S)

7.4.1 Primary analysis of the primary endpoint(s)

The primary endpoint will be analysed in combination with the primary approach of handling ICEs (see [Section 5.1](#)). The FAS is the main analysis set for the analysis of efficacy: the patient set includes all patients who had at least one baseline measurement of 10 hour UACR in week -2, -1, or 0 and at least one post-baseline measurement after week 6.

Refer to Section 7.2.2 of the CTP for a description of the statistical analysis for the change from baseline in log transformed UACR measured in 10-hour urine at 20 weeks of trial treatment.

The adjusted mean reduction in log transformed UACR in 10-hour urine from baseline at 20 weeks and its standard deviation will be obtained from MMRM for the placebo and treatment groups. For the MMRM model, derived UACRs at baseline, visit 6, visit 7, and EoT, which were described in [Section 6.6.2.1](#), will be used.

SAS code for **the MMRM model** will be based on the following structure:

```
PROC MIXED DATA=alldat cl method=reml;

CLASS visit trt subject;

MODEL chg = base*visit visit*trt typediabetes SGLT2ibase / ddfm=kr s CL;
REPEATED visit / subject= subject type=un r rcorr;

LSMEANS visit*trt / pdiff=all om cl alpha=0.05 slice=visit;

RUN;
```

In the event of model non-convergence, the methods described in [Section 10.1](#) will be attempted (in order) to overcome it.

Multiple Comparisons Procedure - Modelling (MCP-Mod) Analysis

For the primary analysis, the dose-response relationship will be modelled using the total daily doses: 3 mg, 6 mg, and 9 mg. The multiple comparison procedure will then be implemented using optimal contrast tests which control the family-wise type I error rate at a one-sided $\alpha = 0.05$. For the MCPMod test, the optimal contrasts of each candidate model are calculated using the R-function optCont.

For the final evaluation, the contrast will be provided using the expected model means from the candidate set and the estimated variance-covariance matrix extracted from the MMRM model.

Once the significance of a dose-response signal is established, the dose-response profile and the target dose can be estimated using a model averaging approach for significant models.

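### The SAP's choice of MMRM visits and the 'after week 6' FAS rule together leave patients who stop between weeks 2 and 6 out of the primary analysis, although their Visit 4 UACR is collected

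*Protocol*

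**What the plan says.** **Sampling.** In the protocol's main flow chart, the row "UACR 10-hour urine sample" has an entry at Visit 4 (week 2). The UACR and eGFR sampling flow chart, row "10-hour urine Sample after FMV", places it on the two days before that visit. Nothing is scheduled at Visit 5; the next collections belong to Visits 6 (week 6), 7 (week 12) and 8 (week 18), week 19 and EoT.

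**Model.** The protocol synopsis states "The analysis will include the fixed, categorical effect of treatment at each visit", and Protocol 7.2.2 has the same structure with an unstructured covariance. Neither names the visits. SAP 7.4.1 does: "For the MMRM model, derived UACRs at baseline, visit 6, visit 7, and EoT". SAP Table 6.6.2.1: 1 has the same columns. No reason is given for leaving out Visit 4.

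**Analysis set.** Protocol 7.2.2: "The primary analysis will be performed on the FAS". Protocol 7.2.1 requires for the FAS a baseline value and "at least one post-baseline measurement after week 6". SAP 7.4.1 repeats this.

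**Missing data.** Under the primary approach, data after treatment discontinuation are dropped and treated as missing at random (Protocol 7.2.2). SAP 6.6.2.1 puts it this way: "The statistical model assumes that patients who had an ICE would have behaved similarly to those who remained in the study". The same section says that a patient with a single post-baseline assessment can enter the model.

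**Changes.** SAP Section 4: "This section is not applicable as no change has been made".

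**The concern.** Missing at random is always conditional on the data in the model. A patient who took drug for two weeks, gave the Visit 4 samples and stopped before Visit 6 has an observed response. The primary analysis does not use it, so it treats that patient's missing week-20 value as explained by baseline and arm alone.

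Early loss could well relate to response. Dose groups 2 and 3 step up at week 2, and group 3 again at week 4. Protocol 1.2 names hypotension among the most frequent drug-related events in the earlier patient trial. If the patients who leave differ in early UACR response from those who stay, the week-20 arm means shift. These means feed MCPMod and are compared with the 0.22 proof-of-concept margin. The documents do not show which way the shift would go: losing strong responders understates the effect, and losing weak responders overstates it.

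A second gap comes from the FAS rule. Visit 6 is the week 6 visit and its samples are taken on the two days before it. Read literally, "at least one post-baseline measurement after week 6" also drops patients whose only on-treatment value is Visit 6. That sits poorly with using Visit 6 in the model and with the SAP's remark on patients with one post-baseline assessment.

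**Working it through.** **1. What each rule does to a patient who stops between Visits 4 and 6**

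| Source | Consequence |
|---|---|
| Flow charts | On-treatment 10-hour UACR at Visit 4 only |
| Protocol 6.2.4 | No UACR at an early EoT visit that does not fall on a scheduled visit |
| Protocol 7.2.2 | Values after discontinuation are not used |
| SAP Table 6.6.2.1: 1 | Visit 4 is not in the model |
| Protocol 7.2.1, SAP 7.4.1 | Outside the FAS unless some UACR exists after week 6 |

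The last two rows both have to change. One exception applies: the FAS text does not say that the later measurement must be on treatment. A patient who stops early and completes FUp2 or FUp3 (two and four weeks after EoT) could qualify through an off-treatment sample, and would then be in the FAS with no usable value.

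**2. Inputs for size**

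The documents state no SD, dropout rate or correlation, so these are assumptions: SD 0.6, correlation ρ between visits 0.4 to 0.6, loss f of 5, 10 or 15% of an arm between weeks 2 and 6, and log-odds of loss rising by 1 per SD of response (odds ratio e^1 = 2.7). As a check on the SD, simulating the MCPMod test with the five candidate shapes in Protocol 7.5 and 60 per group gives the stated 88.5% power at an SD of about 0.68. The biases below scale by 0.68/0.6 = 1.13 at that value.

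**3. Bias with the plan as written**

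Let x be the standardised response that drives loss, p(x) = 1/(1 + exp(−(a + x))), with a set so that the mean of p is f. Among those who stay, the mean of x shifts by δ = |E[x(1 − p(x))]|/(1 − f). The bias in the arm mean at week 20 is SD × ρ × δ.

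| Loss f | δ | Bias, ρ = 0.4 | Bias, ρ = 0.6 |
|---|---|---|---|
| 5% | 0.047 | 0.6 × 0.4 × 0.047 = 0.011 | 0.6 × 0.6 × 0.047 = 0.017 |
| 10% | 0.091 | 0.022 | 0.033 |
| 15% | 0.133 | 0.032 | 0.048 |

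The largest entry is 0.048/0.22 = 22% of the proof-of-concept margin and 0.048/0.35 = 14% of the assumed 9 mg effect. The bias in a comparison with placebo is the difference between the two arms' biases, so it cancels if loss and selection are the same in both.

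**4. Effect of each change**

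Simulation at SD 0.64, ρ = 0.5, 10% loss driven by the Visit 4 value:

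| Analysis | Bias |
|---|---|
| SAP visits, FAS as written | 0.029 |
| Visit 4 added, FAS as written | 0.029 |
| Visit 4 added, FAS widened | 0.000 |

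The formula in step 3 gives 0.64 × 0.5 × 0.091 = 0.029 for the first row.

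**5. If loss follows a later, unobserved response**

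Suppose loss depends on the week-4 response, which is not sampled. Conditioning on Visit 4 then leaves about ρ(1 − ρ) × SD × δ, a fraction 1 − ρ of the bias: 0.60 at ρ = 0.4 and 0.40 at ρ = 0.6. Simulation gives 0.62 and 0.41. At 10% loss and SD 0.6, about 0.6 × 0.4 × 0.6 × 0.091 = 0.013 remains at either correlation.

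**6. If loss is unrelated to response**

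There is no bias. The variance of an arm mean falls by a factor 1 − ρ²f. With ρ = 0.6, 15% active loss and 4% placebo loss, the factors are 0.946 and 0.986. The variance of the difference, in units of SD²/60, goes from 1/0.85 + 1/0.96 = 2.218 to 1.113 + 1.027 = 2.140, so the standard error is about 2% smaller.

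**The case against.** **An undeclared change?** A reader might infer that the SAP contradicts the protocol and conceals it behind "This section is not applicable as no change has been made". The documents do not support that. The wording in the synopsis and Protocol 7.2.2 describes treatment-by-visit terms, not a visit list, and the SAP's declared role is to fill in such detail. Leaving out week 2 also fits a protocol FAS built on data after week 6.

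**Is the visit list alone to blame?** A reader might also infer that adding Visit 4 to the model is enough. It is not. The protocol's own FAS removes most of these patients, and step 4 shows the bias unchanged while that rule stands.

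**Does Visit 4 repair the missing-at-random assumption?** Only if loss depends on the Visit 4 value itself. At Visit 4 every group is still on the common 1 mg TID starting step or placebo, and later loss may follow the titration steps. With visit-specific treatment means and an unstructured covariance, the common step puts no constraint on the week-20 means. It can lower the correlation with week 20, and step 5 shows the resulting limit. This objection stands in part.

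**Is early loss large?** The documents do not say. Protocol 1.2 describes doses up to 3 mg TID as generally well tolerated, and down-titration is not an intercurrent event, so down-titrated patients stay in the analysis. At 5% loss the bias is below 0.02. A flattened dose-response curve is one possibility among several; neither direction nor dose gradient is established.

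**Are there sensitivity analyses?** SAP 6.6.2.1 refers to them, and parts of SAP 7.4 are not visible in the public text. Supplementary 1 uses all available data after discontinuation, but SAP 5.1 ties it to the same Table 6.6.2.1: 1, so it does not bring in Visit 4.

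**Conclusion.** The point holds as a joint effect of two rules. The SAP's visit list and the FAS requirement for a measurement after week 6 together exclude on-treatment data that the trial collects, so for patients who stop between weeks 2 and 6 the missing-at-random assumption conditions on baseline alone. Read literally, the FAS rule also excludes patients whose only on-treatment post-baseline values are from Visits 4 and 6. This is an unexplained choice in the SAP combined with a protocol definition, not a proven departure from the protocol.

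The size is modest and conditional: roughly 0.01 to 0.05 log units in an arm mean at 5 to 15% response-related loss, and zero if loss is unrelated to response. All of this rests on assumed SD, correlation, loss and selection strength. The case for acting is that the remedy uses data already collected, reduced the bias in every response-dependent scenario examined, and is cheap.

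**What to change.** 1. Define the FAS for the primary analysis as a baseline 10-hour UACR plus any post-baseline, on-treatment (before any intercurrent event) 10-hour UACR, Visit 4 included. This also settles whether Visit 6 alone qualifies and whether off-treatment follow-up samples count.
2. Add a Visit 4 column (mean of the scheduled Visit 4 samples, before any intercurrent event) as the first post-baseline level in SAP Table 6.6.2.1: 1 and in the PROC MIXED data. Keep visit*trt, base*visit and type=un. Pass only the EoT means and their covariance to MCPMod, as now.
3. Apply the same to first morning void, using that endpoint's own values.
4. List the MMRM visits explicitly and record both changes, with reasons, in SAP Section 4 before unblinding.

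Steps 1 and 2 must be made together.

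**Cost.** No new data. The FAS change alters a protocol definition, so it needs a documented change and not only a SAP edit. The covariance grows from 3 × 4/2 = 6 to 4 × 5/2 = 10 parameters, which a trial of 240 should support; the SAP already plans for non-convergence. Patients who stop before Visit 4 still contribute nothing, and dependence on a later unobserved response is only partly addressed.
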